
test scores over time) in patients receiving biologic therapies.
 
Definitions: Adherence rates will be defined as: high (>80% of puffs), moderate (50-80% of puffs) and low levels (<50% of puffs) of adherence to maintenance inhalers (assuming an expected baseline usage of two puffs per day).
		
non-adherence to inhaled therapies and lead to incorrect conclusion that the biologic is not effective. In addition, little is known about how patients with severe asthma utilize their inhalers once biologics are initiated and more importantly if it is safe to discontinue these therapies altogether.

To determine the impact on inhalation parameters on categorical response to biologics. Response will be categorized as non-response, partial and complete response on the basis of six factors: a 50% reduction in exacerbations, any reduction in maintenance OCS dose, change of at least 10% in FEV1, improvement of 3 points in ACT score and patient perception of global improvement in asthma.
	
 • Proportion of patients achieving non-response, partial and complete response to biologics. 
Tests: Summary, chi-squared test, and Tukey’s HSD test statistics of inhalation parameters by response group.
	
Response to biologics is heterogeneous, and it is unclear if inhalational parameters measured by the Digihaler™ are correlated with degree of response.

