5 STUDY POPULATION

5.1 INCLUSION CRITERIA

1. A history of severe persistent asthma as defined by ERS/ATS criteria which includes the presence of poor asthma control on high dose ICS/LABA OR the need for high dose ICS/LABA to maintain asthma control OR oral steroids for maintenance therapy for more than 50% of the prior year.
2. Age >18 years of age or older.
3. Presence of current biologic use or planned initiation of biologics following study enrollment.
4. Patients will be categorized on the basis of asthma control (ACT < 19 will be considered poor asthma control). We will cap the patients with good asthma control at 30% and will no longer enroll those patients once the strata have been fully enrolled.
5. Willingness to switch maintenance inhalers to AirDuo® Digihaler™ and/or to use ProAir® Digihaler™ for rescue therapy. Use of nebulized albuterol will be discouraged but not prohibited. We will require patients to document nebulizer use. Patients that discontinue Pro-Air will be asked to document use of their rescue inhalers in their diaries.
6. Can read and communicate in English and is familiar with and is willing to use his/her own smart device and download and use the study application. If their smart device is not compatible with the study software; willingness to use an alternative device that will be provided by the study team.
7. Ability to provide informed consent.
8. The patient must be willing and able to comply with study requirements and restrictions and to remain at the investigational center for the required duration during the study period, and willing to return to the investigational center for the follow-up procedures and assessments as specified in this protocol.

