6.4 STUDY INTERVENTION COMPLIANCE

We will determine medication compliance by assessing the data collected from the inhaler. These inhalational parameters and medication use data will be transferred from the Digihaler™ to the patients' phone app and then to the server powering the dashboard. If a patient switches to ProAir® Digihaler™ /Airduo™ and determines that one of the inhalers is ineffective they can switch back to their original inhaler and remain in the study. The patient will need to agree to use at least one of the two digital inhalers to remain in the study (ie either the rescue or maintenance inhaler) as this will allow us to obtain the inspiratory parameters required in this study. We also ask that all non-digital inhaler use be documented in the patient diary. We will allow a maximum of 10% of the study population to switch their medications during the study.

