6.5 CONCOMITANT THERAPY

6.5.1 RESCUE MEDICINE

The patients will utilize the ProAir® Digihaler™ for rescue. Nebulized albuterol and atrovent will be allowed for severe symptoms during exacerbations and patients will be required to report when these medications were utilized. We will encourage preferential use of the inhaler if symptoms are not severe enough to warrant nebulized medications.

Any concomitant medication a patient is taking at screening and up to the final visit will be recorded on the CRF. Trade name and international nonproprietary name (if available), indication, dose, and start and end dates of the administered medication will be recorded.

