7 STUDY INTERVENTION DISCONTINUATION AND PARTICIPANT DISCONTINUATION/WITHDRAWAL

7.1 DISCONTINUATION OF STUDY INTERVENTION

Patients will be discontinued from study intervention if they are no longer willing or able to comply with study procedures or if they withdraw consent. If a patient switches to ProAir® Digihaler™ /Airduo™ and later has a preference for their original controller or short-acting beta agonist, then switches will be allowed as long as the patient remains on at least one of the two digihaler devices. The patient will need to agree to use at least one of the two digital inhalers to remain in the study (ie either the rescue or maintenance inhaler) as this will allow us to obtain the inspiratory parameters required in this study.

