3. Patients will be assigned to one of three adherence groups (low, moderate, high) based on Digihaler™ inhalation usage parameters over the previous month. We will use the Chi-squared test to determine if group differences exist for each asthma outcome over the next month, and Tukey's Honest Significant Difference test to determine which groups are significantly different.

4. Patients will be assigned to one of three biologics response groups (non, partial, complete) based on six asthma factors (described earlier). We will use the Chi-squared test to determine if group differences exist for each inhalation parameter, and Tukey's Honest Significant Difference test to determine which groups are significantly different.

5. To develop an algorithm that can predict patients that will respond to biologics regression or classification models. Since we expect our training set to be relatively small with a low event rate, we plan to use the entire inhalation parameter dataset for model training but will employ repeated k-fold cross-validation to reduce variance (over-fitting) and include non-linear features to reduce bias (under-fitting). We do not know a priori whether regression or classification would be the appropriate approach to this question so we will test models using both approaches. The classification approach can be formulated as either a two-class problem – Non vs. Partial or Complete responders, or Non or Partial vs. Complete responders – or a three-class problem – Non vs. Partial vs. Complete. The regression approach requires a two-class formulation using logistic regression. Different models will be fit for different formulations and the performance of each model assessed and compared to others.

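### The adherence grouping in 9.4.3 item 3 has no rule for months off the AirDuo Digihaler, so read literally it classes patients who switched to another controller as low adherence.

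*Combined protocol and SAP*

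**What the plan says.** Section 9.4.3 item 3 sets the grouping rule: "Patients will be assigned to one of three adherence groups (low, moderate, high) based on Digihaler™ inhalation usage parameters over the previous month". The groups are then compared on asthma outcomes over the following month.

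Section 3 gives the cut-offs. High is above 80% of puffs, moderate is 50 to 80%, and the last band is "low levels (<50% of puffs) of adherence to maintenance inhalers (assuming an expected baseline usage of two puffs per day". The three bands cover every value from 0 to 100%.

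On the source of the data, Section 6.4 says: "We will determine medication compliance by assessing the data collected from the inhaler". The same section provides that a patient who "determines that one of the inhalers is ineffective they can switch back to their original inhaler and remain in the study". Section 7.1 confirms that "switches will be allowed as long as the patient remains on at least one of the two digihaler devices". Section 6.4 also caps switching at 10% of the study population.

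Two other sources would show what a patient took after a switch. Section 6.4 says: "We also ask that all non-digital inhaler use be documented in the patient diary". For concomitant medication on the CRF, Section 6.5.1 says that "start and end dates of the administered medication will be recorded". Neither source is mentioned in 9.4.3.

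**The concern.** The protocol deliberately keeps patients who have gone back to a non-digital controller, yet the adherence rule can see only Digihaler puffs. Such a patient may take maintenance treatment regularly and still show no AirDuo use. The plan has no not-evaluable category, no minimum amount of data, and no denominator that allows for time off the device.

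This matters because Section 3 wants to learn whether poor adherence to inhaled treatment explains an apparent failure of the biologic. A low group that includes regular users of another controller no longer means low adherence. These patients may also differ from the rest, since perceived ineffectiveness is a named reason for switching back. If they do as well as adherent patients, the contrast between groups shrinks. If poor control drove the switch, their poor outcomes are put down to low adherence. The endpoint giving the proportion of patients at each adherence level is affected in the same way.

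**Working it through.** **Plan figure.** The plan gives no design figure for the adherence comparison. Its sample-size figures (Section 9.2) concern mean peak inspiratory flow and the AUROC, and neither depends on this point.

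**Inputs from the documents.** Two puffs per day; low below 50%, moderate 50 to 80%, high above 80% (Section 3). Grouping on the previous month, outcomes in the next (9.4.3 item 3). Switching cap 10% (6.4). Sample of 100 patients (9.2). Participation of 12 months (1.1).

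**Step 1: the rule on its own.** Take a 30-day month and a patient who takes every AirDuo puff until the switch. The expected number of puffs is 2 × 30 = 60. With d days on the device, the rate is 2d/60.

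| Days on AirDuo | Rate as written | Class | Rate per on-device day |
|---|---|---|---|
| 0 | 0/60 = 0% | low | not defined |
| 14 | 28/60 = 46.7% | low | 28/28 = 100% |
| 15 | 30/60 = 50.0% | moderate | 30/30 = 100% |
| 24 | 48/60 = 80.0% | moderate | 48/48 = 100% |
| 25 | 50/60 = 83.3% | high | 50/50 = 100% |

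The patient's behaviour on the device is the same in the last four rows. Only the switch date moves the class.

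**Step 2: number of patients.** The cap gives 0.10 × 100 = 10 patients. It covers switches of either inhaler, so 10 maintenance switchers is a ceiling. If half the switches are of the rescue inhaler, the number is 5.

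**Step 3: share of the low group, as an illustration only.** The documents give no switch rate, no switch timing and no expected adherence distribution. Assume no dropout, 11 grouping months per patient (the twelfth supplies outcomes only), pooled patient-months, and a true low share L that is the same in switchers and others. Let m patients switch at the end of month t.

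Misplaced patient-months = m(11 − t)(1 − L). Low-group patient-months = 100 × 11 × L + misplaced.

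With L = 20%, the first term of the low group is 220:

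| Switch after month | m = 10 | m = 5 |
|---|---|---|
| 3 | 64/284 = 22.5% | 32/252 = 12.7% |
| 6 | 40/260 = 15.4% | 20/240 = 8.3% |
| 9 | 16/236 = 6.8% | 8/228 = 3.5% |

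The result is sensitive to L. For m = 10 and t = 6, L = 10% gives 45/155 = 29.0%, and L = 40% gives 30/470 = 6.4%.

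These shares show how far the low group could be diluted. They do not show how far the outcome contrast would move, which would need outcome assumptions that the documents do not support.

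**The case against.** The strongest reply is that the zero is inferred. No section says that absent AirDuo records count as zero puffs, and an analyst could treat such a month as missing. That is correct, so a reader who concludes that the plan prescribes zero-filling goes too far. What remains is that the plan offers three exhaustive groups, a fixed denominator and no alternative. Two analysts could therefore place the same patient differently, and the literal reading gives the wrong group.

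A second reply is that the information needed to recognise a switch is collected, through the diary and the CRF medication dates. This is also true, and it makes the repair cheap. It does not make the repair unnecessary, because no analysis section uses either source for the adherence rate.

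A third is that the cap keeps the problem small. It does limit the number of patients. The low group is smaller than the whole sample, however, so its dilution can exceed 10%.

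Two further inferences are tempting and should not be drawn:

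- Inclusion criterion 5 ("Willingness to switch maintenance inhalers to AirDuo® Digihaler™ and/or to use ProAir® Digihaler™ for rescue therapy") might suggest a set of patients on ProAir alone from entry, and so off AirDuo all year. The Synopsis and Sections 6.1.1 and 6.1.2 describe both inhalers being supplied, so this route is too uncertain to carry a figure.
- The mean daily AirDuo doses in the primary endpoint might be thought to be pulled down by off-device days. Section 9.4.2 does not say that such days enter as zeros.

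**Conclusion.** The point holds as a gap in the adherence rule that, on a literal reading, gives the wrong class to patients whom the protocol chooses to keep. A full month off AirDuo is classed low whatever other controller is taken, and the switch-month class follows the calendar. This part needs only the stated rule, a 30-day month and full use until the switch.

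The size is bounded but not known. At most about 10 of 100 patients are affected, and fewer if some switches are of the rescue inhaler. The percentages in the working rest on assumed switch numbers, timing and adherence. The direction of bias cannot be stated in advance, no sample-size figure changes, and the documents do not support saying that the adherence comparison is invalid. Severity is minor to moderate: one secondary comparison and the adherence-proportion endpoint.

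**What to change.** Amend 9.4.3 item 3 as follows, before the initial analysis described in 9.4.6:

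- Compute adherence only over days on which the AirDuo Digihaler is the patient's controller, with two puffs per such day as the denominator. Days on which AirDuo is the controller but is not taken still count as missed puffs, so true non-adherence stays in the rate.
- Identify those days from the medication start and end dates on the CRF (6.5.1). The Schedule of Activities has asthma medication reviewed at all 14 contacts.
- Treat a month with no on-device days, or fewer than a minimum set in advance, as not evaluable. A partial switch month that meets the minimum is kept.
- Report how many patients and patient-months are set aside, and show diary-recorded controller use in those months separately.

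The cost is a few sentences and no new data collection. The comparison becomes slightly smaller and applies to time on AirDuo. Because switchers may not be typical, setting their off-device months aside is itself a selection, which is why the counts and the diary data should be shown.

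### The adherence rule makes no provision for months off AirDuo: applied as written, it classes patients on a non-digital controller as low adherence

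*Combined protocol and SAP*

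**What the plan says.** **Grouping rule.** Section 9.4.3, item 3, allocates patients to a low, moderate or high adherence group "based on Digihaler™ inhalation usage parameters over the previous month". Asthma outcomes over the following month are then compared between the groups.

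**Definition.** The objectives table in section 3 sets high adherence above 80% of puffs, moderate at 50 to 80%, and the last group as "low levels (<50% of puffs) of adherence to maintenance inhalers". The denominator is fixed by "assuming an expected baseline usage of two puffs per day".

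**Who may be off AirDuo.** Inclusion criterion 5 in section 5.1 asks for "Willingness to switch maintenance inhalers to AirDuo® Digihaler™ and/or to use ProAir® Digihaler™ for rescue therapy", so its wording admits a patient who takes only the rescue device. Under section 6.4, patients who judge one of the inhalers ineffective are told that "they can switch back to their original inhaler and remain in the study". Section 7.1 adds that "switches will be allowed as long as the patient remains on at least one of the two digihaler devices". The only limit is in section 6.4: "We will allow a maximum of 10% of the study population to switch their medications during the study".

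**What is not said.** Section 9.3 defines a single analysis population with no AirDuo-user subset. Section 6.4 asks for diary entries of non-digital inhaler use, but no section brings the diary into the adherence calculation. No section says how a month without AirDuo is to be handled.

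**The concern.** The numerator can come only from the AirDuo Digihaler, while the denominator stays at two puffs a day for everyone. A patient who takes another controller faithfully therefore looks the same as one who takes no controller at all. The low group becomes a mixture of true non-adherers and patients treated with something else.

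Section 3 justifies this objective on two grounds: poor adherence to inhaled therapy may be mistaken for failure of the biologic, and it is unknown whether inhaled therapy can safely be stopped. Both depend on the low group being patients who really take little controller medication. If patients on another controller are counted there and do well, their results could be read as evidence that stopping controllers is harmless.

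The error would reach hypothesis 3 in section 9.1, the first secondary endpoint in the synopsis (proportions by adherence rate), the descriptive summaries by adherence group in section 9.4.5, and the subgroup analysis in section 9.4.7.

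**Working it through.** **The plan's own figure.** No sample size or power is stated for the adherence comparison. The figure of 100 patients rests on the precision of mean peak inspiratory flow: 1.96 × 15/√100 = 2.94, which agrees with the stated plus or minus 3. It supplies N = 100 below and nothing else.

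**Inputs from the plan.** Two expected puffs per day and cut-offs of 50% and 80% (section 3); one-month look-back (section 9.4.3); switching cap of 10% (section 6.4), which is 10 of 100.

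**Step 1: score for a month off AirDuo.** Expected puffs in 30 days = 2 × 30 = 60, so low is fewer than 30. No AirDuo use gives 0/60 = 0%: low.

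**Step 2: score for a part-month.** Perfect AirDuo use for *d* days, then another controller, gives 2*d*/60.
- *d* = 14: 28/60 = 47%, low.
- *d* = 20: 40/60 = 67%, moderate.
- High requires 2*d*/60 > 80%, that is, more than 24 days.

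**Step 3: share of the low group misclassified.** Assume *L* truly low patients, and *k* patients off AirDuo for the whole period who all adhere to another controller. Share = *k*/(*L* + *k*). With *k* = 10:
- *L* = 20: 10/30 = 33%
- *L* = 30: 10/40 = 25%
- *L* = 40: 10/50 = 20%

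The reported proportion in the low group would be (*L* + 10)/100, which is 30% instead of 20%, or 50% instead of 40%: ten percentage points too high.

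**Step 4: sensitivity to the assumptions.** Suppose instead that 20% to 50% of the 90 AirDuo users are truly low, so *L* = 18 to 45. The share is 10/28 = 36% to 10/55 = 18%. If a third of the ten are themselves truly low, it is 6.7/28 = 24% to 6.7/55 = 12%. With only five patients off AirDuo, *L* = 19 to 47.5 and the share is 5/24 = 21% to 5/52.5 = 10%.

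**Step 5: direction of bias.** Observed difference = (*L* × *p*_low + *k* × *p*_off)/(*L* + *k*) − *p*_high. For illustration, assume monthly outcome risks of 0.30 (truly low) and 0.15 (high), a true difference of 0.15, with *k* = 10 and *L* = 18 to 45.
- *p*_off = 0.15: (5.4 + 1.5)/28 − 0.15 = 0.096, to (13.5 + 1.5)/55 − 0.15 = 0.123. The difference shrinks.
- *p*_off = 0.30: 0.15. No bias.
- *p*_off = 0.45: (5.4 + 4.5)/28 − 0.15 = 0.204, to (13.5 + 4.5)/55 − 0.15 = 0.177. The difference is inflated.
- No true effect (risk 0.20 in all AirDuo users) and *p*_off = 0.40: (3.6 + 4)/28 − 0.20 = 0.071, to (9 + 4)/55 − 0.20 = 0.036. A false difference appears.

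**The case against.** **No section says in words that these patients are low.** A patient without an AirDuo Digihaler has no maintenance Digihaler data, and an analyst might reasonably treat the month as missing. That stands as a limit: the low label is what the rule yields when applied literally. But the plan offers three groups, one analysis population and no exclusion, so an analyst who set these months aside would be adding an unwritten rule after seeing the data.

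**Rescue-only entry may be rare.** It rests on one and/or in inclusion criterion 5, whereas the synopsis and sections 6.1.1 and 6.1.2 describe supplying both inhalers. This stands. A reader might infer that a large rescue-only stratum would make most of the low group wrong. The documents give no count of such patients and no reason to expect many, so no figure can be attached to them.

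**Ten reverters is a ceiling.** The cap covers all switches, and section 7.1 includes a return to the patient's own short-acting reliever. A patient who drops only ProAir uses up part of the cap but still has valid AirDuo data. The look-back is monthly, so months before a switch are unaffected. Both points stand, and the 33% to 20% must be read as a worst case.

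**The bias need not hide a difference.** A reader might infer dilution toward no difference, as misclassification often produces. The documents do not support that: section 6.4 ties reverting to an inhaler judged ineffective, which could go with worse outcomes and inflate the difference.

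**The data to sort this out are already collected, and the comparison is secondary.** True. This makes the gap cheap to close but does not close it.

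**Conclusion.** The concern holds in a bounded form. The written rule scores months off AirDuo as 0% and part-months too low, so it places patients who use another controller in the low group whatever their use of it. This overstates the low-adherence proportion if they are in fact adherent. It also biases the low-versus-high comparison toward no difference if they do well and away from it if they do badly; there is no bias only if such patients are absent or have the same outcomes as truly low adherers.

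The worst case under the switching cap is 33% to 20% of the low group misclassified. It assumes 100 patients, all ten permitted switchers off AirDuo for the whole period and adherent to another controller, and 20 to 40 truly low patients; the plan does not give that last range. Fewer or later controller switches, or reverters who are themselves poor adherers, make it smaller. Rescue-only entrants would add to it by an unknown amount. This should be corrected before analysis, but it affects a secondary comparison and not the study's primary description of inhaler use.

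**What to change.** In section 9.4.3, item 3:
- Compute adherence only for patient-months in which the AirDuo Digihaler is the controller, and count expected puffs only over days on AirDuo. The dates can be taken from the concomitant-medication start and end dates that section 6.5.1 already requires.
- Class all other months as *not assessable by Digihaler*, outside the three groups, and report how many there are and the asthma outcomes in them.
- Run a sensitivity analysis that classifies those months from the patient diary.

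Carry the same rule into the adherence-proportion endpoint and the summaries in section 9.4.5.

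**Cost.** A short addition to the text and a controller flag per patient-month. The adherence analysis loses patient-months: up to about 10% from reverters, more if there are rescue-only entrants. Leaving out months after a post-baseline switch may introduce selection, because switching may be related to outcome; this is why the outcomes in the omitted months should be shown. The sensitivity analysis relies on self-report, which the study set out to improve on, and the schedule of activities has no diary row, so completeness of the diary should be reported with it.
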